4.1. Ethics Committee

The materials of the clinical trial (including the Protocol, Informed consent form, and materials provided to the patient) will be approved by the Ethics Committee of the Ministry of Health of the Russian Federation before the start of the study. All amendments to the Protocol and updated versions of the Informed consent form will also be submitted to the Ethics Committee.

The clinical trial will be conducted in accordance with the Protocol approved by the Ethics Committee.

4.2. Informed consent form

Informed consent will be obtained from all prospective study participants before any research procedures are initiated. Prior to this, the Investigator must fully inform a patient about all aspects of clinical research, including its purposes, study procedures, expected risks and benefits of participation, and voluntariness of participation.

The patient must be provided with written information about the study (Informed consent form), approved by the Ethics Committee. The patient's informed consent form contains all information about the planned clinical trial, as well as the terms of

confidentiality and the use of the patient's data. The rights, safety, and well-being of the participants will take priority and prevail over the science and society interests. If necessary, information about the procedure for obtaining informed consent from patients/volunteers can be submitted to the Ethics Committee.

Prior to the patient's participation in the clinical trial, two copies of the Informed consent form with the patient's name must be signed and personally dated by the patient or the patient's legal representative, or by a person who conducted the informed consent discussion. One copy of signed and dated written Informed consent form will be provided to the patient, and the other will be kept by the Investigator.

When the patient's condition does not allow him/her to express his/her will and there is no legal representative and the need for treatment is urgent, the question of medical intervention in the interest of the patient and his/her inclusion in the study is resolved by a council of physicians, and if it is not possible – by his/her attending (duty) physician with following notification of the Principal Investigator, officials of the clinical site and the legal representative.

The Informed consent form must be reviewed and approved by the Ethics Committee. The final version of the Study Protocol and Informed consent form must be approved by the Russian Ministry of Health and the Local Ethics Committee (if any) at the clinical site.

All subsequent amendments to the above-mentioned documents will also be submitted for approval to these institutions. In addition, these same institutions will be informed about all adverse events associated or possibly related to the use of the study drug.

The information obtained during the study that may reveal the patient's identity will be kept secret and can only be disclosed within the limits established by law.

5. TRIAL AIM

Assessment of the efficacy and safety of single-bolus intravenous injection of Fortelyzin® in comparison with bolus infusion of Actilyse® in patients with massive PE.

6. TRIAL OBJECTIVES

- To assess the efficacy of single-bolus intravenous injection of Fortelyzin® in comparison with bolus infusion of Actilyse® in patients with massive PE.
- To assess the safety and possible adverse events of single-bolus intravenous injection of Fortelyzin® in comparison with bolus infusion of Actilyse® in patients with massive PE.

7. TRIAL POPULATION

Description of the trial population

This trial is planned to involve adult patients of both sexes aged 18 years and older with a verified diagnosis of massive PE.

7.1. Inclusion criteria

- Men and women aged 18 and older.
- Massive PE (confirmed by CTPA).
- Signs of RV overload/dysfunction (at least one)³ associated with persistent hypotension or shock⁴.

³

- RV end-diastolic diameter more than 30 mm (parasternal long axis);
- RV/LV end-diastolic diameters ratio more than 0.9;
- hypokinesis of RV-free wall (Mc Connel sign);
- tricuspid regurgitant jet velocity in systole more than 2.6 m/s [1, 2].

⁴

- cardiac arrest;
- obstructive shock (systolic BP <90 mmHg or vasopressors required to achieve a BP \geq 90 mmHg despite an adequate filling status, in combination with end-organ hypoperfusion);
- persistent hypotension (systolic BP <90 mmHg or a systolic BP drop \geq 40 mmHg for >15 min, not caused by new-onset arrhythmia, hypovolaemia, or sepsis) [1, 2].

- Patient consent to use reliable contraceptive methods throughout the study and for 3 weeks after:
 - women who have a negative pregnancy test and use the following contraceptives: intrauterine devices, oral contraceptives, contraceptive patch, long-acting injectable contraceptives, double barrier method of contraception. Women who are not capable of bearing children (documented conditions: hysterectomy, tubal ligation, infertility, menopause for more than 1 year) can also take part in the study;
 - men using barrier contraceptives. The study may also include men who are not capable of bearing children (documented conditions: vasectomy, infertility).
- Signed and dated informed consent from the patient to participate in the trial.

7.2. Exclusion criteria

- Increased risk of bleeding:
 - extensive bleeding at present or within the previous 6 months, hemorrhagic diathesis;
 - intracranial (including subarachnoid) hemorrhage at present or in history, suspicion of a hemorrhagic stroke;
 - hemorrhagic stroke or unknown etiology stroke in anamnesis;
 - ischemic stroke or transient ischemic attack within the last 6 months, with the exception of the current acute ischemic stroke within 4.5 hours;
 - central nervous system diseases in anamnesis (including neoplasms, aneurysm, surgery on the brain or spinal cord);
 - major surgery or major trauma within the previous 3 months, recent traumatic brain injury;
 - prolonged or traumatic cardiopulmonary resuscitation (> 2 min), labor within the previous 10 days, recent puncture of an uncompressible blood vessel (eg, subclavian or jugular vein);
 - severe liver disease, including liver failure, cirrhosis, portal hypertension (including esophageal varices) and active hepatitis;

- confirmed peptic ulcer of the stomach or duodenum within the last three months;
- a neoplasm with an increased risk of bleeding;
- simultaneous treatment with oral anticoagulants, for example, warfarin with INR>1.3;
- arterial aneurysms, defects in the development of arteries / veins;
- severe uncontrolled arterial hypertension;
- acute pancreatitis;
- bacterial endocarditis, pericarditis;
- suspicion of a dissecting aortic aneurysm;
- any other conditions, in the opinion of the doctor, associated with a high risk of bleeding.

- Lactation, pregnancy
- Known hypersensitivity to Actilyse®, Fortelyzin®.

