1. BACKGRAUND FOR THE TRIAL

Pulmonary embolism (PE) is a complex clinical problem. The prevalence of PE is high and reaches 30-40 people per 100 000 populations in Russia [1]. PE is one of the leading causes of death, morbidity and hospitalization in Europe [2]. It has been shown that in six EU countries (population about 450 million people), the mortality rate from PE is higher than from AIDS, breast cancer, prostate cancer and road traffic accidents combined, and is 11% of the entire population surveyed [2].

In the Russian Federation, mortality from PE is very high and ranges from 10-30%, depending on modern diagnostics and the use of adequate methods of treatment, primarily thrombolytic therapy.

The indication for thrombolytic therapy is massive PE, defined by size scales and risk stratification. Massive PE is defined in the presence of signs of shock or hypotension, which corresponds to III-V class PESI [1].

In accordance with European [1] and Russian [2] Guidelines for massive PE treatment, the following thrombolytic drugs are used:

- 1) streptokinase according to the standard scheme of administration for 12-24 hours or accelerated scheme for 2 hours;
- 2) urokinase according to the standard (12-24 hours) or accelerated schemes for 2 hours;
- 3) alteplase according to the standard scheme of 100 mg for 2 hours.

The recently completed PEITHO study used the «gold standard» thrombolytic therapy for acute ST-segment elevation myocardial infarction (STEMI) tenecteplase in patients with intermediate-risk PE with signs of right ventricular (RV) disease according to a single bolus administration at a dose of 30-50 mg, depending on body weight. Tenecteplase was shown to be highly effective, combined with a large number (6.3%) of hemorrhagic stroke, which did not allow tenecteplase to be included in the list of recommended thrombolytics for PE [3].

FRIDOM 1 study showed equal efficacy and safety of Fortelyzin®, 15 mg as a single bolus, regardless of body weight, compared with Metalyse® (tenecteplase), administered as a single bolus of 30-50 mg depending on body weight, in patients with STEMI. This study demonstrated the high efficacy of Fortelyzin® and its safety, the absence of major bleeding and hemorrhagic stroke in patients with STEMI complicated by cardiogenic shock [5, 6].

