Fortelyzin®, given as a single bolus of 10 mg regardless of body weight, was non-inferior to Actilyse® (alteplase) bolus infusion at a dose of 0.9 mg/kg (maximum 90 mg) for patients with acute ischemic stroke within 4.5 hours of symptom onset in a recently completed FRIDA trial. Mortality, symptomatic intracranial hemorrhage, and serious adverse events did not differ significantly between groups [7].

These results were decisive for resolving the issue of the possibility of using Fortelyzin® in patients with massive PE accompanied by shock and hypotension, where thrombolytic therapy is the method of choice.

Taking together, the purpose of this trial is to evaluate the efficacy and safety of the Fortelyzin® with its single bolus administration in comparison with the bolus-infusion administration of the Actilyse® in patients with massive PE.

Rationale for the Fortelyzin® dose in patients with massive PE

The FRIDOM1 study Fortelyzin® was used as a single bolus injection of 15 mg in patients with STEMI, including patients with cardiogenic shock. Thrombolytic therapy with Fortelyzin® at a dose of 15 mg in these patients showed high efficacy and safety.

The proposed comparison drug Actilyse® is the «gold standard» in the massive PE treatment. It used at a dose of 100 mg, the same as for STEMI.

In this regard, the dose of Fortelyzin® should be identical to that used for STEMI, 15 mg administered as a single bolus.

Thus, Fortelyzin® in patients with massive PE can be considered justified in comparison with Actilyse® as the “gold standard” for PE thrombolytic therapy.

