The second mechanism of Forteplase® fibrin selectivity results from the difference in the inhibition rate of the plasmin-Forteplase® complex in the bloodstream and on the surface of fibrin, i.e. on the clot. This complex is neutralized by α_2 -antiplasmin in blood plasma 100 times faster than on the fibrin surface.

Fibrin selectivity of Fortelyzin® increases the therapeutic efficacy and prevents the activation of circulating plasminogen, and may also increase the safety of thrombolytic therapy by minimizing exposure to circulating blood fibrinogen.

The thrombolytic fibrin selectivity also causes its dose-dependent effect. The dose of the moderately selective thrombolytic – Actilyse® is 100 mg for STEMI patients and 90 mg for patients with ischemic stroke, while the dose of the fibrin-selective thrombolytic – Fortelyzin® – is 15 mg for STEMI and 10 mg for ischemic stroke.

Also, Fortelyzin® does not cause the formation of neutralizing anti-staphylokinase antibodies in the blood. In rare cases, the transient formation of anti-drug antibodies (in low titers) may be observed.

After intravenous administration of Fortelyzin®, there is a slight decrease in blood fibrinogen, less than 10 %, within 1 day after administration.

Fortelyzin® has a short half-life. The main organ for excretion of the drug (75%) is the liver.

Pharmacokinetics of a single bolus injection of Fortelyzin® at a dose of 15 mg for STEMI patients showed a short half-life ($t_{1/2\alpha}$) of 5.7 minutes and $t_{1/2\beta}$ in the so-called terminal phase of 30 minutes.

Pharmaceutical form: Lyophilizate for preparation of a solution for intravenous administration.

One vial of Fortelyzin® contains:

Active substance: Forteplase® (a recombinant protein containing the amino acid sequence of staphylokinase), 5 mg (745,000 IU).

Excipients: L-arginine – 15,0 mg, L-histidine – 2,0 mg, glycine – 30,0 mg, povidone -17 – 20,0 mg, polysorbate-20 – 0,4 mg.

Solvent: 5mL ampule of sodium chloride 0.9% solution for injection.

The results of Fortelyzin® preclinical studies

Preclinical study of toxicological properties was conducted in E.I. Chazov Russian Cardiology Research Complex of the Ministry of Health of the Russian Federation in accordance with the requirements set out in the “Manual on Experimental (Preclinical) Study of New Pharmacological Substances” (Moscow, 2005) of the Federal Service for Surveillance in Healthcare and Social Development of the Russian Federation.

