9.1.3. Physical examination

Physical examination should be performed by the investigator. It includes (at a minimum) assessment of the patient's general condition and the following body systems: lymph nodes, mouth, and pharynx, lungs, cardiovascular system, abdominal cavity, extremities, musculoskeletal system, nervous system, and skin.

All changes considered clinically significant should be reported as an anamnesis before the study drug administration, and after the patient received the study drug, all changes should be reported as adverse events.

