10. THERAPY DURING THE TRIAL

Study drug: Fortelyzin®

Manufacturer: «SuperGene», LLC, Russia

Drug description

Pharmaceutical form: lyophilizate for preparation of a solution for intravenous administration, supplied with a solvent

Detailed description:

Lyophilizate: tablet-like freeze-dried mass of white or almost white color.

Solvent: colorless transparent liquid.

Reconstituted solution: colorless, transparent or slightly opalescent liquid.

Composition:

Active substance: Forteplase® (recombinant protein containing the amino acid sequence of staphylokinase) 5 mg (745 000 IU).

Excipients: L-arginine – 15,0 mg, L-histidine – 2,0 mg, glycine – 30,0 mg, povidone-17 – 20,0 mg, polysorbate-20 – 0,4 mg.

Solvent: 5mL ampule of sodium chloride 0.9% solution for injection

Dosage regimen: Fortelyzin® will be assigned at a dose of 15 mg (2 235 000 IU).

Route of administration: intravenously in the form of a single bolus injection for 10-15 sec. The solution of Fortelyzin® is prepared immediately before administration: the content of a 5 mg vial (745 000 IU) is diluted in 5 ml of 0.9% sodium chloride solution. Non-storable!

Labeling: «Product for clinical trial only».

Active Comparator: Actilyse®**Manufacturer:** Boehringer Ingelheim Pharma GmbH & Co. KG**Drug description****Pharmaceutical form:** lyophilizate for preparation of a solution for infusion supplied with a solvent.**Detailed description:**

Lyophilizate: freeze-dried mass of white or light yellow color.

Solvent: colorless transparent liquid

Composition:

Active substance: Alteplase 50,0 mg

Excipients: L-arginine: 1742 mg,

Phosphoric acid, 85 %: up to pH 7,2 ± 0,2,

Polysorbate 80: 3,5-5,0 mg.

The excess is 3,5 % of the nominal amount of the active ingredient and excipients in the vial.

Residual traces: gentamicin (used in the production process).

Each vial of solvent contains:

Water for injection: 50 ml

1 ml of the solution after dilution contains 1 mg of alteplase.

Dosage regimen:

Actilyse® is administered in accordance with the instructions for use in ischemic stroke at a dose 100 mg.

Labeling: «Product for clinical trial only».

Previous treatment

Every effort should be made to find out what treatment the patient received within 30 days before administration of the study drug. The names of the drugs, the start and end dates of their use should be registered in the CRF.

Permitted concomitant therapy

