In the first 24 hours after thrombolysis, the use of drugs to lower blood pressure is allowed: angiotensin-converting enzyme inhibitors and angiotensin receptor antagonists. If blood pressure drops during thrombolysis, the use of vasopressors (dobutamine, dopamine, and norepinephrine) is allowed.

Patients treatment is carried out in accordance with current Guidelines [1, 2].

After thrombolysis, anticoagulant therapy with unfractionated heparin must be started within 48 hours:

– intravenously with a bolus of 80 units/kg (or 5000 units) and infusion at an initial rate of 18 units/kg/h (or 1250-1300 units/h), then dose selection according to aPTT values. The goal is to maintain an aPTT of 1,5 to 2,5 times the laboratory-specific upper limit of normal (or anti-Xa activity values of 0,6 to 1,0 units/mL using the amidolytic method).

If anticoagulant therapy with unfractionated heparin is initiated at the prehospital stage, an intravenous bolus is not administered, but its infusion is continued.

After 48 hours, a switch is made to low molecular weight heparin, which is administered for 7 days:

– Enoxaparin sodium – subcutaneously 100 units (1 mg/kg) 2 times a day followed by indirect anticoagulants:

– Vitamin K antagonists – orally, dose selection in order to maintain the INR in the range from 2 to 3;

or NOACs:

– Dabigatran etexilate – 150 mg orally 2 times daily;

– Rivaroxaban – 15 mg orally 2 times a day for 21 days, then 20 mg once daily;

– Apixaban – 5 mg orally 2 times daily.

Anticoagulants are taken for at least 6 months.

In case of an allergic reaction during thrombolysis, the use of glucocorticoids and antihistamines is permitted.

In case of severe bleeding (especially from non-compressible vessels), the administration of thrombolytics should be discontinued. The administration of fresh frozen plasma or fresh blood is indicated.

Prohibited concomitant therapy

In patients with massive PE, massive fluid resuscitation is not recommended because aggressive volume loading may worsen right ventricular dysfunction.

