12. SAFETY ENDPOINTS

- Safety outcomes – ischemic and hemorrhagic strokes within 7 days;
- Safety outcomes – bleedings BARC type 3 and 5;
- number and severity of SAEs and AEs in organs and systems.

Adverse events

Adverse event (AE) is an unfavorable medical occurrence in a patient administered a pharmaceutical product, which may not have a causal relationship with its use. Thus, an AE can be any adverse symptom (including deviation of the laboratory value from the norm), a complaint, or a disease, the time of occurrence of which does not exclude a causal relationship with the use of the medicinal product, regardless of the presence or absence of such communication.

Information about AEs should be collected at each visit by interviewing the patient, as well as during physical examination and evaluation of laboratory and instrumental data. All AEs that occur during the trial should be evaluated and documented.

When registering an adverse event, the following information should be reflected, if possible:

- the exact time of AE occurrence и разрешения

- the nature of the AE
- severity (mild, moderate, severe)
- causal relationship with the study drug
- whether the AE is serious
- actions taken (whether AE required any therapeutic measures)
- outcome

AEs Grading:

- **Mild:** the presence of signs or symptoms that do not affect daily activities.
- **Moderate:** AE has sufficient intensity to interfere with daily activities.
- **Severe:** inability to work or perform daily activities.

The connection between the development of AE and the use of the study drug is determined by the WHO scale:

- ***definitely related:*** Clinical manifestations of AE, laboratory findings deviations that occur during the period of drug administration, cannot be explained by the presence of existing diseases and the influence of other factors. Manifestations of AE regress after the drug discontinuation and occur again after repeated administration.
- ***Probable.*** Clinical manifestations of AE, laboratory findings deviations are associated with the time of drug administration, unlikely to be related to concomitant diseases or other factors, and which regress with drug withdrawal. Response to the drug re-challenge is unknown.

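### A patient with a current ischemic stroke is eligible, yet the plan's only Fortelyzin data in stroke patients are at 10 mg and this trial gives 15 mg

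*Combined protocol and SAP*

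**What the plan says.** The exclusion list in Section 7.2, repeated word for word in the Protocol Summary, groups its first block of criteria under raised bleeding risk. One of them covers ischemic stroke or TIA in the preceding 6 months, "with the exception of the current acute ischemic stroke within 4.5 hours".

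On Fortelyzin dose, the document distinguishes indications:

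- Section 1 cites a completed trial in acute ischemic stroke, treated within 4.5 hours of onset: "Fortelyzin®, given as a single bolus of 10 mg regardless of body weight".
- Section 2 gives the dose by indication: it "is 15 mg for STEMI and 10 mg for ischemic stroke".
- Section 10 fixes the dose here: "Fortelyzin® will be assigned at a dose of 15 mg (2 235 000 IU". No adjustment is given for a patient with a current stroke.
- The dose rationale at the end of Section 1 reasons that Actilyse uses the same dose in PE as in STEMI, so Fortelyzin should too. Stroke does not enter the argument.

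On Actilyse, Section 1 lists among the recommended PE treatments "alteplase according to the standard scheme of 100 mg for 2 hours". Section 2 gives 100 mg for STEMI and 90 mg for ischemic stroke. Section 10 sets 100 mg for this trial, although that line refers to the stroke labelling.

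**The concern.** The criterion points two ways. A TIA five months ago keeps a patient out because of bleeding risk, while an infarct now in progress does not. The exempted patient may then be randomised to a Fortelyzin dose above the one the document gives for ischemic stroke, and the plan offers no reason why 15 mg is acceptable in that setting. At stake is the exposure of a few patients, possibly none, to a dose for which the document has no supporting data in their condition. The point concerns eligibility and patient safety; the primary analysis does not depend on it.

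**Working it through.** The point rests on the text and on dose ratios. No sample-size, power or alpha figure is involved.

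**1. The plan's own dose figure.** One vial holds 5 mg (745,000 IU). Three vials give 3 × 5 = 15 mg and 3 × 745,000 = 2,235,000 IU, which agrees with Section 10.

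**2. Fortelyzin, trial dose against stroke dose.** Inputs: 15 mg (Section 10) and 10 mg (Sections 1 and 2). Both are independent of body weight, so the ratio is the same for every patient: 15 / 10 = 1.50.

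**3. Actilyse, trial dose against stroke dose.** Inputs: 100 mg (Section 10) and 90 mg (Section 2). Ratio: 100 / 90 = 1.11. Section 1 describes the stroke regimen as 0.9 mg/kg up to 90 mg, so 1.11 is the minimum and applies from 90 / 0.9 = 100 kg upward. For a lighter patient the ratio is larger: at 74 kg it is 100 / (0.9 × 74) = 100 / 66.6 = 1.50. The size of the ratio therefore does not by itself single out the Fortelyzin arm. The difference between the arms is that 100 mg of alteplase is the document's standard treatment for PE, whereas 15 mg of Fortelyzin in PE is what the trial is testing.

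**4. What the 15 mg evidence covers.** In the randomised STEMI trial described in Section 2, 191 patients were allocated to Fortelyzin 15 mg and there was no intracranial hemorrhage. These were STEMI patients, so the result says little about giving 15 mg into an acute infarct of the brain.

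**5. How many patients.** The documents give no prevalence of concurrent acute ischemic stroke in massive PE. Assume 0% to 1%:

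| Assumed prevalence | Of 310 randomised | Expected in the Fortelyzin arm (155) |
|---|---|---|
| 0% | 0 | 0 |
| 1% | 310 × 0.01 = 3.1 | 155 × 0.01 = 1.55 |

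So 0 to about 3 patients are affected, of whom about half would receive Fortelyzin 15 mg.

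**The case against.** **The exemption may be deliberate and may never be used.** It appears identically in two places, and its window matches that of the cited stroke trial. To qualify, a patient must have massive PE with hypotension or shock, complete CTPA, echocardiography and venous ultrasound, and still be within 4.5 hours of stroke onset. The doctor must also not invoke the exclusion for suspected hemorrhagic stroke or the general clause on high bleeding risk. This stands as an argument about frequency: the count is probably near zero. It does not supply a reason for 15 mg, the general clause is discretionary and sits beside an explicit exemption, and the hemorrhagic-stroke exclusion does not reach a known ischemic stroke. A reader might suspect that the phrase was carried over from a stroke protocol, but the documents do not establish that.

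**A dose ratio is not a risk.** This stands. Nothing in the document links 1.5 times the dose to more bleeding, and a reader who infers harm at 15 mg goes beyond the text.

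**Two further inferences are tempting and should not be drawn.**

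- Section 12 counts "ischemic and hemorrhagic strokes within 7 days" as a safety outcome, so a reader might infer that baseline strokes would corrupt that comparison. Section 9.1.3 answers most of this: "All changes considered clinically significant should be reported as an anamnesis before the study drug administration". The baseline examination includes the nervous system, later changes are recorded as adverse events with their time and nature, and all bleeds are registered and graded. The section has no rule for adjudicating strokes, but that is true for every patient, and deleting the exemption would not provide one.
- Section 10 says "anticoagulant therapy with unfractionated heparin must be started within 48 hours". A reader might infer that stroke patients must be given early heparin. The text sets an outer limit and leaves room for delay.

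**Conclusion.** The concern holds on dose and safety alone. The plan admits a patient with a current ischemic stroke under a criterion meant to limit bleeding, and may give that patient 1.5 times the Fortelyzin dose that its own stroke evidence covers, without a stated reason. Actilyse 100 mg also exceeds the stroke dose, by a factor of at least 1.11, but that is the regimen the document gives as standard for PE.

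This is a minor point. The figure of 0 to 3 of 310 rests entirely on an assumed prevalence of 0% to 1%, and zero is plausible. The documents show no excess harm. A reader might infer that the non-inferiority comparison is compromised; the documents do not support that. Such patients would be randomised like any others, they are few at most, and 7-day death from any cause is ascertained in the same way whether or not a stroke was present at entry.

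**What to change.** Delete the exempting phrase from Section 7.2 and from the exclusion criteria in the Protocol Summary. Any ischemic stroke or TIA in the preceding 6 months, including a current one, then excludes the patient.

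If the sponsor wants to keep these patients, the alternative is to state why 15 mg is acceptable during an acute ischemic stroke. Adding baseline brain imaging or a stroke scale would not answer the dose question, so deletion is the cleaner choice.

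The cost is a protocol amendment, which under Sections 4.1 and 4.2 goes to the Ethics Committee and the Ministry of Health; it could be combined with other changes. On the assumption above, 0 to 3 patients become ineligible. Enrolment still runs to 310, so power is unchanged. The rare patient with PE shock and a concurrent stroke would be treated outside the trial at the physician's discretion.
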